| OU | Both Eyes |
| PDGF | Platelet Derived Growth Factor |
| PT | Preferred Term |

| | |
|--------|---|
| SAE | Serious Adverse Event |
| SD-OCT | Spectral Domain Optical Coherence Tomography |
| SE | Study Eye |
| SOC | System Organ Class |
| Tie2 | Tyrosine kinase with immunoglobulin-like and epidermal growth factor-like |
| VEGFR2 | Vascular Endothelial Growth Factor Receptor 2 |
| VEGF | Vascular Endothelial Growth Factor |
| VE-PTP | Vascular Endothelial Protein Tyrosine Phosphatase |

1. SYNOPSIS

| | |
|--|----------------------|
| Sponsor: AsclepiX Therapeutics, Inc. | |
| Name of Investigational Product: AXT107 | Study Phase: 1/2a |
| Name of Active Ingredients: AXT107 is a 20-mer synthetic peptide derived from the non-collagenous domain of collagen IV that inhibits VEGF-A, VEGF-C and activates Tie2. | |
| Study Title: Phase 1/2a Study of the Safety and Bioactivity of AXT107 in Subjects with Diabetic Macular Edema (DME) – CONGO study | |
| Objectives: Primary Objective: To evaluate the safety and tolerability of a single injection of three dose levels (0.1 mg/eye, 0.25 mg/eye, or 0.5 mg/eye) of AXT107 in subjects with DME Secondary Objective: To evaluate the bioactivity and duration of action of AXT107 for the treatment of DME | |
| Methodology: This is an open-label, dose-escalating, 48-week study assessing the safety, tolerability, bioactivity and duration of action of a single intravitreal injection of 0.1 mg (low dose), 0.25 mg (mid dose), or 0.5 mg (high dose) AXT107 in approximately 18 subjects (up to 6 subjects per dose) with DME. Upon providing informed consent, subjects will be sequentially enrolled into the study. Decision regarding dose escalation will be based on the recommendation from the Data Monitoring Committee (DMC). The first 3 eligible subjects will receive the low dose of AXT107 injection. After the 3 low dose subjects complete a 7-day follow-up, the DMC will review their safety data. If an acceptable safety profile is determined by the DMC, 3 additional subjects will be enrolled to receive the mid dose of AXT107 injection. Upon completion of a 7-day follow-up, review of the safety data, and determination of an acceptable safety profile by the DMC for the mid dose subjects, 3 additional subjects will be enrolled to receive the high dose of AXT107 injection. For the first 9 subjects, treatment naïve patients CANNOT be enrolled. After the 9 initial subjects have completed the 7-day follow-up, 9 additional subjects (3 each to receive the low dose, mid dose, and high dose of the study drug) who can be previously treated or treatment naïve may be enrolled. In total, approximately 18 subjects with DME will be enrolled and will be followed for 48 weeks. If the maximum tolerated dose (MTD) is not reached after the 0.5 mg group, a higher dose up to 1.0 mg may be tested. All subjects will attend a total of 16 visits: Screening (Day -14 to -1), Baseline (Day 0), Day 1 (Phone call), Week 1, Week 4, Week 8, Week 12, Week 16, Week 20, Week 24, Week 28, Week 32, Week 36, Week 40, Week 44 and Week 48. Stopping rules will be considered upon DMC decision if any of the following events are identified: 
Decrease in Early Treatment Diabetic Retinopathy Study (ETDRS) best corrected visual acuity (BCVA) of ≥ 15 letters (3-line decrease) unrelated to the natural progression of the disease and determined by the Investigator to be related to the study drug in ≥ 2 subjectsIntraocular inflammation (anterior or posterior) grade +2 or more in ≥ 2 subjects (using SUN Grading Working Group and Nussenblatt et al grading)Increase in intraocular pressure (IOP) to ≥ 30 mmHg for more than 24 hours post-injection in ≥ 2 subjects despite IOP lowering medication treatment | |

- Any other serious ocular or systemic adverse event (AE) that, in the opinion of the Investigator, is related to the study drug in ≥ 1 subject

Rescue therapy with the Investigator's preferred treatment will be allowed starting at Week 12 for any subject who has received injection of AXT107 and for whom there is ≥ 7 letter ETDRS BCVA decrease from Baseline (Day 0) or ≥ 75 μ m increase in Central Subfield thickness (CST) compared to the lowest previous visit.

Number of Subjects:

Approximately 18 subjects with diabetic macular edema secondary to type 1 or type 2 diabetes mellitus will be enrolled. The final number of subjects enrolled may be adjusted based on the presence of dose limiting toxicities.

Duration of the Study:

The expected duration of this clinical study is up to 50 weeks, including a 14-day screening phase and 48 weeks of on treatment/ follow up phase.

Inclusion and Exclusion Criteria:

Inclusion Criteria:

1. 18 years of age or older
2. Type 1 or 2 diabetes mellitus with center-involved DME and with central subfield thickness ≥ 305 μ m (females) or 320 μ m (males) on Spectralis® Spectral Domain Optical Coherence Tomography (SD-OCT) device or 290 μ m (females) or 305 μ m (males) on Cirrus® SD-OCT device and with intraretinal or subretinal fluid as evidenced by Spectral Domain Optical Coherence Tomography (SD-OCT) in the study eye at Screening, as confirmed by the Investigator
3. BCVA in the study eye at Baseline (Day 0) between 65 and 23 ETDRS letters (20/40 and 20/320 Snellen equivalent) with BCVA decrement determined by the Investigator primarily attributable to DME
4. BCVA of 34 ETDRS letters or better (20/200 or better Snellen equivalent) in the non-study eye at Baseline (Day 0)
5. Able and willing to give signed informed consent and follow study instructions

Exclusion Criteria:

1. Any signs of high risk proliferative diabetic retinopathy in the study eye and related complications, as determined by the Investigator
2. Previously treated patients who are non-responders to anti-VEGF determined by the Investigator
3. Panretinal photocoagulation within 6 months or macular laser photocoagulation within 3 months from Screening in the study eye
4. Use of intraocular or periocular corticosteroids within 4 months (with the exception of fluocinolone acetonide intravitreal implant which is excluded), Aflibercept within 8 weeks, Ranibizumab and Bevacizumab within 6 weeks from Baseline (Day 0) in the study eye
5. Any concurrent disease that would require medical or surgical intervention during the study in the study eye (e.g. retinal detachment, significant cataract, uncontrolled glaucoma)
6. Any condition that may preclude improvement in visual acuity or affect the evaluation of the study eye after resolution of DME (e.g. vitreous hemorrhage, macular ischemia, pre-retinal fibrosis involving the macula, pre-retinal macular hemorrhage, visually significant vitreomacular traction, or media clarity insufficient to obtain quality images)
7. Chronic uveitis or ongoing clinically significant infection or inflammation (e.g. keratitis, scleritis) in either eye
8. Previous vitreoretinal surgery, previous filtration surgery, cataract surgery within 3 months or YAG laser capsulotomy within 1 month of Screening in the study eye
9. History of cataract surgery complications (vitreous loss) or aphakia in the study eye

10. History of penetrating ocular trauma in the study eye
11. History of allergy to fluorescein or povidone iodine
12. History or current systemic condition that preclude the safe administration of the study treatment or confound results (e.g. HbA1c > 12% at Screening, uncontrolled hypertension [$\geq 180/100$] on optimal medical regimen at Screening, systemic anti-VEGF treatment, renal failure requiring dialysis, or renal transplant)
13. Women of childbearing potential who are pregnant, nursing, planning a pregnancy, or not using a medically acceptable form of birth control
14. Participation in an interventional clinical study at Screening

Investigational Product, Dose, and Route of Administration:

Subjects will receive one of the following doses of AXT107 single intravitreal injection in the study eye.

- AXT107 0.1 mg (low dose)
- AXT107 0.25 mg (mid dose)
- AXT107 0.5 mg (high dose)

Control Product, Dose, and Route of Administration:

N/A

Safety Assessments:

- Adverse events (AEs)
- ETDRS BCVA
- IOP
- Slit lamp biomicroscopy
- Dilated fundus exam (DFE)
- Optos (at selected sites only)
- SD-OCT
- OCT-A (at selected sites only)
- Fundus photography (FP)
- Fluorescein angiography (FA)
- Diabetic Retinopathy Severity Scale (DRSS)
- Laboratory evaluation (including ADA assay)
- Vital signs
- Physical examinations
- Pregnancy test

Efficacy Assessments:

- CST (Mean change in CST from Baseline) assessed by SD-OCT and measured by Reading Center
- BCVA (Mean change in ETDRS letters)
- BCVA (Proportion improving ≥ 5 , ≥ 10 , and ≥ 15 letters from Baseline (Day 0))

Statistical Methods:

Sample Size Determination:

Approximately 18 subjects will be enrolled, with 6 subjects in each dose. The final number of subjects enrolled may be adjusted based on the presence of dose limiting toxicities. This sample size is not planned based on statistical considerations.

Analyses:

Age, sex, race, ethnicity, and baseline assessments will be summarized and listed by dose level. Medical history, history of ocular surgery and procedures, and concomitant medication will also be summarized and listed.

Changes from baseline in BCVA (ETDRS letter score) and retinal thickness (CST) will be summarized by dose level using continuous summary statistics. BCVA change will be summarized using categorical summaries as well, including frequency counts and percentages improving at least 5, 10, and 15 letters.

Verbatim descriptions of AEs will be mapped to MedDRA thesaurus terms and be presented in a data listing. Treatment emergent AEs that occur after the first dose of study medication will be summarized by dose level using frequency and percent for each system organ class (SOC) and preferred term (PT) within each SOC. Summaries will be presented separately for ocular and non-ocular AEs. All TEAEs will be summarized by severity and study drug relatedness.

BCVA will be summarized at each time point using both continuous summaries (ETDRS letter score), including change from Baseline (Day 0), and categorical summaries, including change from Baseline (Day 0) on an ETDRS chart in the number of lines.

IOP will be summarized at each time point using both continuous summaries, including change from Baseline (Day 0), and categorical summaries for pre-stated categories of change in IOP.

Slit lamp biomicroscopy and ophthalmoscopy measures will be summarized at each measured time point using categorical summary statistics.

FA will be summarized by visit.

DRSS will be summarized at each measured visit and change from Baseline (Day 0) to each measured visit.

Vital signs will be summarized at each visit and for change from Baseline (Day 0) to each visit using continuous summary statistics by treatment group and visit.

Clinical laboratory results will be summarized using both continuous summaries, including change from Baseline (Day 0), and discrete summaries, including frequency and percent of subjects with an abnormal value and shift tables from Baseline (Day 0). Additionally, laboratory data will be presented in data listings.

Exploratory analyses will be performed to summarize the results obtained from the Notal Vision Home OCT device and home M&S® Technology visual acuity measurement.

3. BACKGROUND

3.1 Introduction

The worldwide prevalence of diabetes was estimated to be more than 8.5% in 2017, for a total of 451 million people affected (Guariguata 2014). With an aging population and increasing prevalence of obesity, it is estimated that 592 million people will have diabetes in 2035. A meta-analysis of 35 population-based studies worldwide suggests that almost 7% of the diabetic population has diabetic macular edema (DME) (Yau 2012). DME occurs due to retinal microvasculature damage, increase in vascular permeability, and loss of blood-retinal barrier leading to interstitial fluid accumulation in the retina, particularly in the region of the macula (Cunha-Vaz 1975, Patelli 2014, Bhagat 2009).

In DME, vascular permeability, angiogenesis, and inflammation play an important role (Campa 2010, Bhagat 2009). Retinal hypoxia and the hypoxia-regulated protein vascular endothelial growth factor (VEGF) play key roles in the pathogenesis of DME (Nguyen 2004, Nguyen 2009). Intravitreal injection (IVT) of a VEGF neutralizing protein, either in the form of an antibody or a chimeric receptor, is first-line treatment for DME and provides benefit in many patients (Nguyen 2006, Nguyen 2012), but there is a substantial percentage of patients (40 to 60%) in whom anti-VEGF injections are not sufficient to eliminate edema or provide a clinically significant improvement in visual acuity (Heier 2014, Korobelnik 2014). These patients may experience permanent reductions in visual acuity over time from the damaging effects of chronic, recurrent edema (Do 2013, Channa 2014). There is thus still an unmet medical need for agents to treat DME using novel mechanisms.

In addition to VEGF inhibition, Tie2 (Tyrosine kinase with immunoglobulin-like and epidermal growth factor-like domains 2) is also being increasingly recognized for its role in regulating vascular permeability. Tie2 is a tyrosine kinase receptor that, like VEGF receptor-2, is located on vascular endothelial cells and has been implicated in the modulation of vascular permeability (Wong 1997, Thurston 1999, Thurston 2000). However, although phosphorylation of VEGF receptor-2 stimulates vascular leakage, phosphorylation of Tie2 activates downstream pathways that suppress vascular leakage and promote vascular stabilization. Angiopoietin 1 is an endogenous full agonist that stimulates phosphorylation of Tie2 (Davis 1996). Angiopoietin 2 is an endogenous weak, partial agonist that competes with angiopoietin 1, thereby suppressing Tie2 phosphorylation (Maisonpierre 1997, Yuan 2009). Tie2 is also regulated by vascular endothelial protein tyrosine phosphatase (VE-PTP), also known as human protein tyrosine phosphatase beta, which is physically associated with Tie2. It dephosphorylates Tie2, thereby reducing Tie2 activation and signaling through the Tie2 pathway (Yacyshyn 2009). Levels of both angiopoietin 2 and VE-PTP are increased by hypoxia, leading to accentuated VEGF-mediated ocular neovascularization and vascular leakage (Hackett 2000, Hackett 2002, Oshima 2004, Oshima 2005, Shen 2014). Preclinical models have shown that VE-PTP inhibition, even in the presence of high angiopoietin 2, restores Tie2 activation (Shen 2014).

The drugs currently used to treat DME are administered IVT and they have a short duration of action; Lucentis® is administered every month and Eylea® is administered monthly initially, and if there is an adequate response it may be dosed every 2 months or administered every 3 months. Frequent dosing is a burden for patients and can also increase the chance of adverse effects related to the injection. Thus, there is a considerable unmet medical need for alternative

treatment options with prolonged treatment duration to reduce treatment burden and new mechanism of action for patients who could not achieve optimal treatment effect from anti-VEGF agents.

AsclepiX Therapeutics, Inc. is developing AXT107 Intravitreal Injection for the treatment of retinal diseases, including diabetic macular edema (DME), neovascular age-related macular degeneration (nAMD), and retinal vein occlusion (RVO). AXT107 is a synthetic 20-mer collagen IV-derived peptide which inhibits Vascular Endothelial Growth Factor Receptor 2 (VEGFR2) and activates the vessel stabilizing tyrosine kinase receptor Tie2. AXT107 disrupts integrin $\alpha v\beta 3$ to inhibit signaling from VEGFR2 and other growth factors, including PDGF, HGF, and IGF; consequently, choroidal neovascularization and vascular leakage are inhibited. AXT107 disrupts $\alpha 5\beta 1$ and stimulates the relocation of Tie2 and the integrin subunit $\alpha 5$ to cell junctions. AXT107 then activates junctional Tie2 by converting the Ang2 that is abundant in these diseases into a strong agonist, thereby upregulating downstream survival signals, rearranging F actin to strengthen junctions, and, as a result, reducing endothelial junctional permeability. In addition, AXT107 resolves TNF α -induced vascular inflammation in endothelial cells by converting the pro-inflammatory Ang2 into a strong agonist of Tie2 signaling, disrupting the synergism between TNF α and Ang2 while also preventing I κ B α degradation directly through Tie2 signaling. This recovery of I κ B α prevents NF- κ B nuclear localization, thereby blocking NF- κ B induced inflammatory responses. Administered intravitreally, AXT107 has anti-angiogenic, anti-permeability, and anti-inflammation effect and induces regression of disease in animal models of retinal neovascularization (Mirando 2020, Silva 2017, Formica 2019).

This Phase 1/2a, open-label, dose-escalating, 48-week study is planned to assess the safety, tolerability, bioactivity, and duration of action of a single intravitreal injection of AXT107 in the study eye of subjects with DME.

3.2 Investigational Product

AXT107 is a 20-mer synthetic peptide made up of naturally-occurring amino acids developed as a first-in-class synthetic peptide that inhibits VEGFR2 and activates Tie2 as a monotherapy agent.

AXT107 will be administered via an intravitreal injection (IVT) to patients with DME. Based on available pharmacodynamic and pharmacokinetics data, three doses, 0.1mg/eye, 0.25mg/eye, 0.5 mg/eye will be tested in this clinical study.

3.3 Summary of Relevant Data

A brief summary of the findings from nonclinical studies is presented below. Please refer to the Investigator's Brochure for detailed study information.

AXT107 was tested in the genetic tet/opsin/VEGF mouse model in which high levels of human VEGF cause massive vascular leakage leading to exudative retinal detachment. In this mouse model, AXT107 prevents retinal detachment more potently than aflibercept. AXT107 also strongly inhibits ischemia-induced retinal neovascularization in an oxygen-induced retinopathy (OIR) model in the mouse. In the rabbit eye nonclinical studies, AXT107 strongly inhibited VEGF induced vascular leakage. Remarkably, in head-to-head studies in which AXT107 was

tested at a human dose equivalent of afibercept in the rabbit eye, AXT107 inhibited vascular leakage more potently than afibercept and its activity lasted at least twice as long as afibercept.

In addition, AXT107 was tested in a retinopathy of prematurity model of angiogenesis in the mouse eyes. The results showed that AXT107 inhibited angiogenesis induced by hypoxia in a dose-dependent manner. This suggested that AXT107 can be used to inhibit neovascularization caused by hypoxia.

Regarding the activation of Tie2, AXT107 was tested in a retinopathy of prematurity mouse model for phosphorylation of Tie2. The study showed that AXT107 induced the phosphorylation of Tie2 when it is present in conditions of hypoxia in which HIF, VEGF and Ang2 are all increased. This result suggested that AXT107 causes an increase in Tie2 phosphorylation in the presence of increased Ang2 which normally causes a decrease in Tie2 phosphorylation.

AXT107 was further tested in a model in which Lipopolysaccharide (LPS) was used to cause vascular leakage in the mouse eye. This model serves as a surrogate for inflammatory diseases of the eye including DME and uveitis. The results demonstrated that AXT107 inhibited LPS induced vascular leakage and has anti-inflammation effect.

Ocular tissue distribution studies have showed the sustained ocular exposure of AXT107 in the retina, choroid, and vitreous of rabbit eyes for up to 12 months.

In the toxicology studies in rabbits and minipigs, AXT107 was well tolerated, no significant ocular toxicity was observed for up to 15 months in rabbits and for up to 9 months in minipigs. No systemic exposure was detected at doses up to 1.0 mg/eye and no systemic toxicity was observed.

In summary, nonclinical studies have demonstrated that AXT107 is more potent than afibercept, has a longer efficacy duration with no detectable systemic exposure.

3.4 Known Risks and Benefits to Human Subjects

This is the first-in-human clinical trial of AXT107. The risks associated with AXT107 are not well understood at this time. The potential risks related to intravitreal injection include conjunctival hyperemia or hemorrhage. Endophthalmitis, vitreous hemorrhage, and retinal detachment are uncommon risks associated with intravitreal injection.

The anticipated benefit of AXT107 as a new treatment option with a different mechanism of action is the potential for a new therapeutic effect with a prolonged duration of action that will ease the burden of frequent treatments for patients with retinal diseases.

3.5 Target Population

The target population for AXT107 is diabetic patients with center-involved diabetic macular edema. In this study, approximately 18 subjects with an existing diagnosis of center-involved DME will be recruited to participate.

4. STUDY OBJECTIVES

The primary objective of this study is to evaluate the safety and tolerability of a single injection of three dose levels (0.1 mg/eye, 0.25 mg/eye, or 0.5 mg/eye) of AXT107 in subjects with DME.

The secondary objective of the study is to evaluate the bioactivity and duration of action of AXT107 for the treatment of DME.

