5.1.1 Study Measures

The Safety measures are as follows:

- Adverse Events
- ETDRS BCVA
- IOP
- Slit lamp Biomicroscopy
- DFE
- Optos (at selected sites only)
- SD-OCT
- OCT-A (at selected sites only)
- Fundus Photography
- Fluorescein Angiography
- Diabetic Retinopathy Severity Scale (DRSS)
- Clinical Labs
- Vital signs
- Physical examination
- Pregnancy testing

The efficacy measures are as follows:

- Change in CST from Baseline (Day 0)
- BCVA (Mean change in ETDRS letters)
- BCVA (Proportion improving ≥ 5 , ≥ 10 , and ≥ 15 letters from Baseline (Day 0)

Refer to [Table I-1 in Appendix I](#) for a schedule of study visits and Procedures.

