5.6 Assessment of Efficacy

5.6.1 Central Subfield Thickness

SD-OCT will be performed for both eyes starting at Screening (Day -14 to Day-1) and at all attended visits. Mean change in CST from Baseline (Day 0) will be assessed.

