5.6.2 Best Corrected Visual Acuity

Mean change in ETDRS letters from Baseline (Day 0) and percentages improving at least 5, 10, and 15 letters will be assessed.

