6.3 Statistical Methods

Age, sex, race, ethnicity, and baseline assessments will be summarized and listed by dose level. Medical history, history of ocular surgery and procedures, and concomitant medication will also be summarized and listed.

Changes from baseline in BCVA and retinal thickness (CST) will be summarized by dose level using continuous summary statistics. BCVA change will be summarized using categorical summaries as well, including frequency counts and percentages improving at least 5, 10, and 15 letters.

Verbatim descriptions of AEs will be mapped to MedDRA thesaurus terms and be presented in a data listing. Treatment emergent AEs, those that occur after the first dose of study medication, will be summarized by dose level using frequency and percent for each system organ class (SOC) and preferred term (PT) within each SOC. Summaries will be presented separately for ocular and non-ocular AEs. TEAEs will be summarized by severity and study drug relatedness.

BCVA will be summarized at each time point using both continuous summaries (ETDRS letter score), including change from Baseline (Day 0), and categorical summaries, including change from Baseline (Day 0) on an ETDRS chart in the number of lines.

IOP will be summarized at each time point using both continuous summaries, including change from Baseline (Day 0), and categorical summaries for pre-stated categories of change in IOP.

Slit lamp biomicroscopy and ophthalmoscopy measures will be summarized at each measured time point using categorical summary statistics.

FA will be summarized by visit.

DRSS will be summarized by visit and change from Baseline (Day 0) to each visit.

Vital signs will be summarized at each visit and for change from Baseline (Day 0) to each visit using continuous summary statistics by treatment group and visit.

Clinical laboratory results will be summarized using both continuous summaries, including change from Baseline (Day 0), and discrete summaries, including frequency and percent of subjects with an abnormal value and shift tables from Baseline (Day 0). Additionally, laboratory data will be presented in data listings.

Exploratory analyses will be performed to summarize the results obtained from the Notal Vision Home OCT device and home M&S® Technology visual acuity measurement.

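### Duration of action is a secondary objective with no endpoint to define it, and Section 6 has no rule for values observed after rescue or other study-eye DME treatment

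*Combined protocol and SAP*

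**What the plan says.** Section 4 gives the secondary objective: "The secondary objective of the study is to evaluate the bioactivity and duration of action of AXT107 for the treatment of DME". Section 3.4 describes the anticipated benefit as "the potential for a new therapeutic effect with a prolonged duration of action".

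The efficacy measures in 5.1.1 and 5.6 are limited to CST and BCVA. For CST, 5.6.1 says: "Mean change in CST from Baseline (Day 0) will be assessed". For BCVA, 5.6.2 says: "Mean change in ETDRS letters from Baseline (Day 0) and percentages improving at least 5, 10, and 15 letters will be assessed". The analysis in 6.3 is: "Changes from baseline in BCVA and retinal thickness (CST) will be summarized by dose level using continuous summary statistics". Section 6.3 also commits to by-visit BCVA summaries: "BCVA will be summarized at each time point using both continuous summaries (ETDRS letter score), including change from Baseline (Day 0"). It names no time points for CST. Home OCT and home visual acuity, collected at selected sites, are summarised as exploratory.

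On rescue, 5.3.3 allows the investigator's preferred treatment from Week 12 when a BCVA or CST criterion is met, and recommends that rescued subjects continue visits to Week 48. Section 5.3.4 prohibits no concomitant medication. In Section 6, the efficacy population is everyone who received study drug (6.1), LOCF fills missing bioactivity values (6.5), and interim analyses follow completion of Weeks 12, 24 and 36 by all subjects (6.6). Rescue is not mentioned in any of these. The nearest safeguard is in 6.3: "Medical history, history of ocular surgery and procedures, and concomitant medication will also be summarized and listed".

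**The concern.** Two gaps combine. First, the objective asks how long the effect lasts, but no listed measure turns the repeated CST and BCVA values into a duration: there is no time to loss of effect, no time to rescue and no treatment-free proportion. AXT107 visibility (5.5.4.4, 5.5.4.9) records whether the product can be seen, not whether it is acting.

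Second, the visits that carry the information on duration are the late ones, and those are the visits at which a subject may already have had another active treatment. If a dose wears off, its subjects tend to meet the rescue criteria, receive an effective drug and improve. Their improved values are then averaged in as results for that dose. The distortion favours apparent durability, which is the property the sponsor hopes to show.

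**Working it through.** There is no power calculation to reproduce: 6.2 defines no hypotheses and 6.4 says the sample size has no statistical basis. The only planned figure is 3 doses × 6 subjects = 18, which agrees.

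**Do post-rescue values enter?** Rescued subjects are advised to stay (5.3.3), so their later values are observed. All treated subjects are analysed (6.1). LOCF acts only on missing values (6.5), so it removes nothing. If a rescued subject later misses a visit, LOCF carries the post-rescue value forward.

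**Which visits?** Appendix I gives 13 in-person post-injection visits: Weeks 1, 4, 8, 12, then 16, 20, 24, 28, 32, 36, 40, 44 and 48. The last nine follow the opening of rescue: 9/13 = 69%. This counts Week 12 values as pre-rescue, which assumes that Week 12 assessments come before any rescue given that day; the documents do not state the order. Earlier visits are exposed only if other DME treatment is given, which 5.3.4 does not bar.

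**Which interim looks?** Under 5.1.3 the first three cohorts are dosed in sequence, each with a 7-day follow-up, before the last nine subjects enrol. Nominally the first subjects are at least 3 × 7 = 21 days ahead of the last nine, before adding DMC review and recruitment time. When the last subject reaches Week 12 (Day 84), the first are at Day 84 + 21 = 105 or later. The Week 16 window opens at 112 − 7 = Day 105. Section 6.6 sets when each look happens but does not limit its data to the named visit, so even the first look can contain post-rescue values.

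**How large?** If *k* of 6 subjects are rescued and rescue changes each value by *d*, the dose mean moves by *k* × *d* / 6 and a responder proportion by up to *k* / 6. The values of *d* are assumptions.

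| *k* of 6 rescued | CST mean, *d* = 50 to 100 µm | BCVA mean, *d* = 5 to 10 letters | Responder proportion, at most |
|---|---|---|---|
| 0 | 0 | 0 | 0 |
| 1 | 8.3 to 16.7 µm | 0.8 to 1.7 letters | 16.7 points |
| 2 | 16.7 to 33.3 µm | 1.7 to 3.3 letters | 33.3 points |
| 3 | 25 to 50 µm | 2.5 to 5.0 letters | 50 points |

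**How likely is at least one rescue in a dose group?** 1 − (1 − *p*)^6 gives 0.74, 0.95 and above 0.99 for assumed per-subject probabilities of 0.2, 0.4 and 0.6.

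**The case against.** This is a first-in-human study with safety as the primary objective, no hypotheses and a sample size chosen without statistics. No error rate or decision rule depends on the point. That stands, and it limits the matter to how the secondary objective is read. It does not supply a definition of duration.

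A reader might infer that the plan yields nothing on duration. That goes too far: by-visit BCVA to Week 48, CST measured at every attended visit and the exploratory home measurements show a time course. What is missing is a defined endpoint. Nor does one rescue spoil every late mean, because summaries are by dose level and the other groups are untouched.

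The opposite inference, that a weak drug effect would rarely trigger CST rescue and so masking is negligible, is not supported either. I simulated unrescued subjects with half effect at Week 1, full effect at Weeks 4 and 8, and linear loss to zero at Week 24. With a 25 µm peak effect, the share meeting the 5.3.3 CST criterion by Week 48 was 0.3%, 12.5% and 44% for measurement-noise SDs of 10, 15 and 20 µm. The answer turns on a noise figure the documents do not give, and the BCVA route was not simulated.

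The concomitant-medication listing would show rescue drugs with dates, which is a real but partial safeguard because it is not linked to the efficacy summaries. The fields named in 5.3.4 do not include the treated eye, although 5.3.2 foresees that both eyes may qualify. The CRF is not among the documents, so that is a query and not a finding.

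**Conclusion.** The point holds. Duration of action has no defining endpoint or analysis, and no rule covers values after rescue or other study-eye DME treatment. Followed as written, the plan lets later summaries for a dose group mix AXT107 with another treatment once a subject in that group is rescued.

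Scheduled visits from Week 16 on are exposed to protocol rescue, earlier ones only to other DME treatment, and all three interim looks can be affected. A reader might take the Week 12 look as safe because rescue only opens then; sequential enrolment and the missing data-cut rule mean that it is not.

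The true size is unknown and may be zero. The illustration of 8 to 17 µm and up to 16.7 points per rescued subject rests on 6 subjects per dose; the CST figure also assumes a rescue effect of 50 to 100 µm. This should be corrected, but it does not threaten the safety objective.

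**What to change.** Make these changes before the first interim analysis, because the study is open-label and rules set after seeing data would look chosen. The rescue rule itself stays as it is.

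1. Add to 5.1.1, 5.6 and 6.3 a descriptive duration endpoint by dose: time from injection to the first visit meeting a pre-stated loss-of-effect criterion used for analysis only, or to first other study-eye DME treatment, whichever comes first. Apply no LOCF to it. Report it beside the number of subjects with a pre-stated initial response; otherwise a subject who never responded, and so has no effect to lose, may be counted as long duration.
2. Report by dose and visit the number free of rescue or other study-eye DME treatment, with a subject listing of treatment dates.
3. In 6.3 and 6.5, present by-visit CST and BCVA summaries both with and without values after rescue or other study-eye DME treatment, next to those counts. In the version without them, do not carry post-treatment values forward and do not let LOCF fill the excluded visits. Count rescued subjects as non-responders in the letter-gain proportions. State that CST is summarised at each visit.
4. As a query only, check that the CRF captures the treated eye and any non-drug rescue procedure, with dates.

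The cost is one endpoint definition, one count table, one listing, a second version of the by-visit summaries, short text edits and a CRF check. BCVA and SD-OCT are already scheduled at every in-person visit.

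The downside is selection. If 3 of 6 are rescued and the other 3 sit at −60 µm, the summary without post-treatment values reads −60 µm, whereas counting the rescued subjects as 0 gives (3 × −60 + 3 × 0)/6 = −30 µm. The counts must therefore stand beside the means. Results also stay imprecise: 3 of 6 has an exact 95% confidence interval of 12% to 88%.
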